5.7.4 Electrocardiogram

Number (%) of subjects experiencing a normal/abnormal electrocardiogram (ECG) assessment will be tabulated by visit for overall subjects.

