7.2.12. Adrenal Laboratory Assessments

A plasma sample for ACTH and cortisol assessments will be collected. These parameters will be measured at Screening (Visit 1), Week 1 (Visit 2), Week 12 (Visit 3), Week 24 (Visit 4), Week 36 (Visit 5), Week 48 (Visit 6), Week 60 (Visit 7), Week 72 (Visit 8), Week 84 (Visit 9), Week 96 (Visit 10), Week 108 (Visit 11), Week 120 (Visit 12), Week 132 (Visit 13), Week 144 (Visit 14, Week 156 (Visit 15), Week 168 (Visit 16), Week 180 (Visit 17), Week 192 (Visit 18), Week 204 (Visit 19), Week 216 (Visit 20), Week 228 (Visit 21), Week 240 (Visit 22 End-of-Treatment/Premature Discontinuation) and at the Post-Treatment Visit (6 weeks post discontinuation of ataluren). These parameters will be analyzed by the central laboratory. The Central Laboratory Manual should be consulted for collection, processing, and shipping details.

Aldosterone and renin pre-treatment values will be measured at Screening (Visit 1), and, as necessary, for patients with treatment emergent evidence of adrenal dysfunction. These parameters will be analyzed by the central laboratory. The Covance Central Laboratory Manual should be consulted for collection, processing, and shipping details.

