7.2.13. Urinalysis

Urinalysis will include analysis for pH, specific gravity, glucose, ketones, blood, protein, urobilinogen, bilirubin, nitrite, and leukocytes. These parameters will be measured at Screening (Visit 1), Week 1 (Visit 2), Week 12 (Visit 3), Week 24 (Visit 4), Week 36 (Visit 5), Week 48 (Visit 6), Week 60 (Visit 7), Week 72 (Visit 8), Week 84 (Visit 9), Week 96 (Visit 10), Week 108 (Visit 11), Week 120 (Visit 12), Week 132 (Visit 13), Week 144 (Visit 14), Week 156 (Visit 15), Week 168 (Visit 16), Week 180 (Visit 17), Week 192 (Visit 18), Week 204 (Visit 19), Week 216 (Visit 20), Week 228 (Visit 21), Week 240 (Visit 22 End-of-Treatment/Premature Discontinuation) and at the Post-Treatment Visit (6 weeks post discontinuation of ataluren). These parameters will be analyzed by the central laboratory. Urine samples will also be collected and shipped to central laboratory for assessment of urine protein, creatinine, osmolality and urinalysis. The Covance Central Laboratory Manual should be consulted for collection, processing, and shipping details.

7.2.14. 12-Lead ECG

A 12-lead ECG will be obtained at Screening (Visit 1) to establish a baseline tracing. Thereafter during the study, ECGs should be obtained as clinically indicated.

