3.4 Sample Size

The sample size, up to ~96 subjects, was determined by how many subjects satisfy all inclusion/exclusion criteria when applying for participation in this study and not by any formal statistical hypothesis.

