5 STATISTICAL ANALYSIS

5.1 General Statistical Considerations

Summary tables for continuous variables will contain the following statistics: n, mean, standard deviation, standard error, 95% confidence intervals (CIs) on the mean, median, minimum, and maximum. Summary tables for categorical variables will include N, n, and percentages. In by-visit summaries, the analysis visits will be derived via visit mapping windows.

By-patient listings will be created for each CRF module. The data will be listed by center/subject ID and visit.

In addition, all analyses will be performed by corticosteroid use (yes or no before or during the study), by ambulatory status (ambulatory or non-ambulatory) at baseline, and overall, unless specified otherwise.

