5.7.2 Laboratory Tests

Hematological, serum biochemistry, adrenal laboratories, and urine data and their changes (only for continuous laboratory parameters) from baseline will be summarized by visit.

Shift tables for hematology and biochemistry data will also be presented showing change in CTCAE severity grade from baseline to each visit. For parameters for which a CTCAE scale does not exist, shift tables will be presented showing change in results from baseline (normal, low and high [or abnormal]) to each visit (normal, low and high [or abnormal]).

Summary of abnormalities in laboratory variables pre-defined for safety monitoring will be done per the following Table 2.

Table 2: Safety Monitoring Parameters and Actions to be Taken

Organ System and Laboratory Parameter	Stop Study Drug Immediately, Confirm Abnormal Value, and Then Start Work-Up	Stop Study Drug After Confirming ^a Abnormal Value, and Then Start Work-Up	Continue Study Drug, Confirm Abnormal Value, and then Start Work-Up ^a
Hepatic			
Serum total bilirubin	\geq Grade 3 ($\geq 3.0 \times$ ULN)	Grade 2 (1.5 – 3.0 x ULN)	---
Serum GGT	\geq Grade 3 ($\geq 5.0 \times$ ULN)	Grade 2 ($>2.5 - 5.0 \times$ ULN)	---
Serum ALT			\uparrow of >150 U/L with stable or \downarrow CK
Adrenal			
Plasma ACTH	---	$>$ ULN (and plasma cortisol $<$ LLN)	$>$ ULN (and cortisol WNL)
Renal			
Serum cystatin C	>2.00 mg/L	$>1.33 - 2.00$ mg/L	---
Serum creatinine	\geq Grade 2 ($\geq 1.5 \times$ ULN for age)	Grade 1 ($>$ ULN – $1.5 \times$ ULN for age)	---
Serum BUN	$\geq 3.0 \times$ ULN	$\geq 1.5 - 3.0 \times$ ULN	---
Urine protein: urine creatinine (spot)	---	>0.40 mg:mg	---
Urine protein: urine osmolality (spot)	---	>0.30 mg/L:mOsm/kg	---
Urine blood (by dipstick)	4+ (Large)	3+ (Moderate)	2+ (Small)

Organ System and Laboratory Parameter	Stop Study Drug Immediately, Confirm Abnormal Value, and Then Start Work-Up	Stop Study Drug After Confirming ^a Abnormal Value, and Then Start Work-Up	Continue Study Drug, Confirm Abnormal Value, and then Start Work-Up ^a
Serum electrolytes	Grade 3-4	Grade 2	Grade 1
Serum Na ⁺ , high	>155 mmol/L	>150 – 155 mmol/L	---
Serum Na ⁺ , low	<130 mmol/L	---	---
Serum K ⁺ , high	>6.0 mmol/L	>5.5 – 6.0 mmol/L	---
Serum K ⁺ , low	<3.0 mmol/L	---	---
Serum Mg ²⁺ , high	>1.23 mmol/L	---	---
Serum Mg ²⁺ , low	<0.4 mmol/L	<0.5 – 0.4 mmol/L	---
Total serum Ca ²⁺ , high	>3.1 mmol/L	>2.9 – 3.1 mmol/L	---
Total serum Ca ²⁺ , low	<1.75 mmol/L	<2.0 – 1.75 mmol/L	---

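### SAP 5.7.4 tabulates normal/abnormal ECG percentages by visit, but after Screening only boys with a clinical indication have an ECG, so the on-treatment rows cannot be compared with the Screening row

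*SAP*

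**What the plan says.** Protocol 7.2.14 sets one ECG for everybody: "A 12-lead ECG will be obtained at Screening (Visit 1) to establish a baseline tracing". It continues: "Thereafter during the study, ECGs should be obtained as clinically indicated". The schedules of events in the protocol (Table 4) and the SAP (Table 1) agree, with a mark at Screening and testing only as indicated after that.

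The planned analysis, in SAP 5.7.4 under Primary Variables, is: "Number (%) of subjects experiencing a normal/abnormal electrocardiogram (ECG) assessment will be tabulated by visit for overall subjects". The section does not define the denominator or treat indicated ECGs separately, and it has no per-boy post-baseline summary. The general rule in SAP 5.1 adds only this: "Summary tables for categorical variables will include N, n, and percentages".

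Renin and aldosterone have a similar sampling pattern. Protocol 7.2.12, whose heading covers the adrenal laboratory assessments as a group, says: "Aldosterone and renin pre-treatment values will be measured at Screening (Visit 1), and, as necessary, for patients with treatment emergent evidence of adrenal dysfunction". SAP 5.7.2 then plans: "Hematological, serum biochemistry, adrenal laboratories, and urine data and their changes (only for continuous laboratory parameters) from baseline will be summarized by visit". It neither names nor excludes renin and aldosterone.

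**The concern.** A by-visit table invites the reader to follow a percentage from baseline through treatment. That works when the same boys are measured at each visit. Here the first row comes from all boys and every later row from those an investigator chose to test. The two kinds of row estimate different things, and a change between them may reflect who was tested.

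The study has a single arm, so comparison with baseline is its main internal reference for safety, and safety is the primary objective. Cardiac findings matter in this population: Protocol Section 9 names QTc limits among the kinds of worsening that may lead to withdrawal. A table that could suggest a cardiac signal where none exists, or hide a real one, should not go into the report without a guard.

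**Working it through.** The documents give no figure for this point, so there is none to reproduce. The check has four parts.

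**1. Who is in each row.** Screening: every boy, up to about 96 (SAP 3.4). Every later visit: only boys with a clinical indication. This comes directly from Protocol 7.2.14 and both schedules.

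**2. How far the percentage can move with no true change.** Let *N* = 96, *p* = the true share abnormal (constant over time), *a* = the chance of an indicated ECG at a visit for a boy with an abnormality, and *b* = the same chance for a boy without one. The documents give none of *p*, *a* or *b*; all three are assumptions.

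- Share abnormal among tested boys = *pa* / [*pa* + (1 − *p*)*b*]
- Share abnormal among all boys = *pa*

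For *p* = 20%, *a* = 30%, *b* = 5%:

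- Abnormal and tested: 96 × 0.20 × 0.30 = 5.76
- Normal and tested: 96 × 0.80 × 0.05 = 3.84
- Tested in total: 9.6
- Among tested: 5.76 / 9.6 = 60%
- Among all: 5.76 / 96 = 6%

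The Screening row would show 20%. Varying the assumptions, with *b* = 5% and *a* from 15% to 50%:

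| True share, constant | Shown, tested boys only | Shown, all 96 | Boys tested per visit |
|---|---|---|---|
| 10% | 25% to 53% | 1.5% to 5% | 5.8 to 9.1 |
| 20% | 43% to 71% | 3% to 10% | 6.7 to 13.4 |
| 40% | 67% to 87% | 6% to 20% | 8.6 to 22.1 |

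If testing is unrelated to ECG status (*a* = *b* = 10%), the tested-only share stays at *p*. The all-boys share still falls, for example from 20% to 2%.

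**3. Which ECGs reach the table.** In SAP 6.1 the baseline window ends on day 1 and the Week 12 window starts on day 42, so days 2–41 have no row. The Week 192 window ends on day 1386 and the next listed window (Week 216) starts after day 1470, so days 1387–1470 have none either. An indicated ECG on those days drops out of the by-visit table. Where a window holds several valid assessments, the last is used, so an abnormal ECG followed by a normal repeat in the same window is shown as normal.

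**4. Renin and aldosterone.** Protocol 7.2.12 groups them with ACTH and cortisol as adrenal laboratory assessments. SAP 5.7.2 summarizes adrenal laboratories without exclusions, so the natural reading includes them. After Screening they are measured only where adrenal dysfunction is suspected, and a by-visit mean change would describe that subgroup alone. ACTH and cortisol are scheduled every 12 weeks and are unaffected.

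**The case against.** The strongest reply is that no particular bias is established. A reader might infer that the abnormal percentage must rise on treatment by construction. The documents do not support that. A rise needs a denominator restricted to boys with an ECG at that visit, and indicated ECGs that are abnormal more often than Screening ECGs. The SAP does not state the first. The second is plausible, but nothing in the documents confirms it. With all boys in the denominator the percentage falls instead. This part of the objection stands, and the direction has to be left open.

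Other outputs also carry ECG information. SAP 5.1 provides by-patient listings for each CRF module, and SAP 5.7.1 counts abnormal ECGs reported as TEAEs. These help but do not repair the table. Under Protocol 8.1.1 an ECG abnormality is an adverse event only if it needs intervention or investigation beyond a repeat test and does not belong to an event already reported. The TEAE count is therefore narrower than the ECG findings, and a listing does not correct a summary percentage.

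On renin and aldosterone, it is fair to say that the SAP does not name them, that continuous summaries print n, and that change from baseline is within boy. No by-visit abnormal percentage is planned for them, since the SAP's shift tables cover hematology and biochemistry only. Protocol 6.3.1 already says that changes in them are to be read alongside other laboratory findings. This part is therefore an inference with lower stakes, although the selection remains.

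Finally, the defined primary endpoint names adverse events and laboratory abnormalities, not ECGs, and no test or stopping rule uses this table. That limits the severity.

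**Conclusion.** The point holds in this form: the on-treatment rows of the SAP 5.7.4 table describe a clinically selected subset and cannot be compared with the Screening row. This follows from the stated schedule and the stated analysis and needs no assumption.

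The direction and size do need assumptions. The percentage is likely inflated with a tested-only denominator and understated with an all-subjects one. The 60% and 6% against a constant 20% are illustrative and rest on assumed prevalence and testing rates. What they show is that the unstated denominator alone can change the reading tenfold. The window gaps and the last-in-window rule are separate faults, read directly from SAP 6.1. The renin and aldosterone part is an inference from how the protocol groups the adrenal tests.

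Severity is minor to moderate: this is a descriptive safety table with no test or decision rule attached.

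**What to change.** In SAP 5.7.4, replace the by-visit percentage with:

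- (a) the Screening ECG result in all boys;
- (b) a per-boy summary from all post-baseline ECGs, regardless of visit window: n/N with any post-baseline ECG, and the number with any ECG newly abnormal relative to Screening. Label it as clinically triggered testing and show both denominators (all As-Treated boys, and boys with a post-baseline ECG);
- (c) a listing of post-baseline ECGs by study day, with the reason for testing if it was recorded. Neither document shows that it was, so this item must be conditional.

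In SAP 5.7.2, exclude renin and aldosterone from the by-visit mean and change-from-baseline tables, and list them by boy with the paired ACTH and cortisol values. Leave ACTH and cortisol as planned.

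The cost is SAP wording and a few changed table shells, using data already collected. The report loses its by-visit ECG table.

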5.8 Secondary Variables

Subject [REDACTED] will be excluded from the As-Treated population in the analyses of all secondary endpoints.

5.8.1 6-Minute Walk Test

The distance walked at each visit and the change from baseline at each post baseline visit, as obtained from the 6-minute walk test (6MWT), will be summarized descriptively for ambulatory subjects with non-missing baseline 6MWT assessments. The distance walked at each will also be summarized for each actual age.

The endpoint will also be analyzed by means of a mixed model repeated measures (MMRM). An unstructured variance-covariance will be assumed and the estimation method will be the default, ReML. The model will include the factors for treatment, visit, age (6-11, 12-17, and ≥ 18 years), use of corticosteroids at baseline (yes vs no), and baseline 6MWD category (< 300 meters, ≥ 300 - < 400 meters, ≥ 400 meters), and baseline 6MWD as a covariate. Visit is considered as a categorical variable. From this analysis the mean change at each visit will be evaluated. If the model cannot converge, compound symmetry variance-covariance structure will be assumed.

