6.2. Study Drug Treatment

6.2.1. Duration of Therapy

Treatment with ataluren in the context of this protocol is anticipated to occur for 240 weeks. The actual duration of ataluren treatment under this protocol will be subject to the following conditions:

- The patient has the right to withdraw consent and discontinue ataluren at any time.
- If the patient's condition substantially worsens after initiating ataluren treatment, the patient
 will be carefully evaluated by the investigator in consultation with the PTC Therapeutics
 medical monitor. The patient will be withdrawn from treatment if continuing would place
 them at risk.
- Upon consultation with the PTC Therapeutics medical monitor, the investigator may withdraw the patient from ataluren treatment, if, in the investigator's clinical judgment, it is not in the patient's best interest to continue.
- The patient will be withdrawn from treatment if he is unable to tolerate ataluren.
- The patient may be withdrawn from this study if he is eligible to participate in another ataluren - nmDBMD clinical study or program.
- This study may be discontinued by the relevant regulatory authority and/or PTC Therapeutics at any time.
- This study may be stopped upon ataluren marketing authorization within the relevant country.

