10.4.6. Secondary Variables

10.4.6.1. 6-Minute Walk Test

The distance walked at each visit and the change from baseline in the distance walked at each

postbaseline visit, as obtained from the 6MWT, will be summarized descriptively. Only the results of the patient's best valid test at each visit will be included in the analysis. Changes from baseline in 6MWD at each postbaseline visit will be analyzed using paired t-tests. All data from the 6MWTs, valid or invalid, will be listed by patient and visit, with invalid results flagged.

The 6MWD at each visit will be converted into a percent-predicted 6MWD value through the use of a relevant reference equation. The percent-predicted 6MWD value at each visit and the change from baseline in the percent-predicted 6MWD value will be summarized descriptively. Only the results of the patient's best valid test at each visit will be included in the analysis. Changes from baseline at each postbaseline visit will be analyzed using paired t-tests. All percent-predicted 6MWD values, valid or invalid, will be listed by patient and visit, with invalid results flagged.

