1 OVERVIEW

This statistical analysis plan (SAP) details the statistical methods to be used in the analyses and presentation of the data collected in Study PTC124-GD-019-DMD, also referred to as Study 019. Preparation of this SAP incorporates statistical design elements present in the protocol Version 5.0 (dated 18 November 2015). Details are documented in Sections 1-7.

In addition to the protocol defined analyses, a natural history control using the Cooperative International Neuromuscular Research Group (CINRG) will be utilized in order to help to better understand the long-term ataluren data. The planned analysis will be presented in Section 8.

After the implement of protocol Version 5.0, the sponsor has developed the protocol Version 6.1 (dated 08 March 2017) specifically for Canadian sites only for ethics approval when they finished all visits per Version 5.0 and were waiting to roll into another open-label nmDMD Study PTC124-GD-016-DMD conducted in the United States (US). The maximal scheduled visit in Version 5.0 was extended from week 240 to week 336 in Version 6.1. All data collected based on both Versions will be summarized together.

Where conflicts exist between this SAP and the study protocols, the information contained in this SAP supersedes the protocol.

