7 ANALYSIS CHANGES FROM PROTOCOL

The paired t-test is removed from the analysis on change from baseline in 6-minute walk test, timed function tests, North Star Ambulatory Assessment, Egen Klassifikation Scale, and spirometry endpoints. Subgroup analyses based on 6-minute walk test, corticosteroid type, and the cumulative duration of corticosteroid use are added.

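### The SAP leaves out the protocol's percent-predicted 6MWD summary without recording the removal, so growth can hide part of the decline in raw distance

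*SAP*

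**What the plan says.** Protocol 10.4.6.1 plans the walk test in two units. After raw distance it adds: "The 6MWD at each visit will be converted into a percent-predicted 6MWD value through the use of a relevant reference equation". It continues: "The percent-predicted 6MWD value at each visit and the change from baseline in the percent-predicted 6MWD value will be summarized descriptively". Paired t-tests on that change and a by-patient listing are planned too. The reference equation is not named.

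SAP 5.8.1 covers distance only: "The distance walked at each visit and the change from baseline at each post baseline visit, as obtained from the 6-minute walk test (6MWT", a summary of distance at each actual age, and a mixed model for repeated measures (MMRM). Besides treatment and visit, the model has a three-level age group, baseline corticosteroid use, a baseline distance category and baseline distance. It has no height term.

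SAP section 7 gives the changes from the protocol. The removal it names is this: "The paired t-test is removed from the analysis on change from baseline in 6-minute walk test, timed function tests" and the other functional scales and spirometry. Its addition is: "Subgroup analyses based on 6-minute walk test, corticosteroid type, and the cumulative duration of corticosteroid use are added". Percent-predicted 6MWD is not mentioned there or anywhere else in the SAP text available.

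SAP section 1 sets the precedence rule: "Where conflicts exist between this SAP and the study protocols, the information contained in this SAP supersedes the protocol". On duration, protocol 6.2.1 says "Treatment with ataluren in the context of this protocol is anticipated to occur for 240 weeks", and SAP section 1 adds for Canadian sites that "The maximal scheduled visit in Version 5.0 was extended from week 240 to week 336 in Version 6.1".

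**The concern.** The patients are boys and young men. The SAP's youngest age group is 6-11 years, and its matched ambulatory populations enter at 9-18 years. Where a boy is still growing, the distance expected of a healthy peer can rise during follow-up, so an unchanged distance in meters can be a falling share of what is expected. Raw change from baseline then adds a growth component to the disease component. With no concurrent control arm, nothing in the design cancels the growth part.

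The protocol planned a supporting analysis that addresses this. If it drops out unrecorded, a reader of the results may take a flat curve in meters for stable disease, and a reader of SAP section 7 would not know that the other view had been planned. If the analysis is instead still owed, the equation remains open and could be chosen after the data are seen, in an open-label study.

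**Working it through.** **Step 1: set the two plans side by side.** There is no power or sample-size figure to reproduce; the sample size rests on no formal hypothesis (protocol 10.1, SAP 3.4).

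| Item | Protocol 10.4.6.1 | SAP 5.8.1 | Listed in SAP 7? |
|---|---|---|---|
| Raw 6MWD, value and change by visit | Yes | Yes | Not applicable |
| Paired t-test | Yes | No | Yes, as removed |
| Percent-predicted 6MWD, value and change by visit | Yes | No | No |
| Raw distance by actual age; MMRM | No | Yes | No |

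Removing the paired t-test takes away a test. It does not account for the missing percent-predicted values or their descriptive change.

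**Step 2: what else in the SAP could remove growth?** The MMRM age factor is a broad group and does not track growth within a boy. The by-age summary shows raw distances and leaves each boy's change unadjusted. Elsewhere the SAP does standardise: percent-predicted FVC and FEV1 use ulna length and age (5.8.5), and blood pressure percentiles under age 18 use age and height (5.7.3).

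**Step 3: are the data there?** In ambulatory patients height is measured at screening and every 24 weeks to week 240 (protocol 7.2.7), the same visits as the walk test (protocol 7.2.16).

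**Step 4: length of follow-up.** Years = weeks × 7 / 365.25.

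- 240 × 7 / 365.25 = 4.60 years
- 336 × 7 / 365.25 = 6.44 years

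**Step 5: illustration of size.** Every input here is assumed, because the documents give no equation, growth rate or walk results. Predicted distance at entry is 550 m, the boy walks 350 m throughout, and predicted distance rises by g meters per year.

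Percent predicted after t years = 100 × 350 / (550 + g × t). At entry it is 100 × 350 / 550 = 63.6%.

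| g (m/year) | Predicted distance at 240 weeks | % predicted at 240 weeks | Change (points) | % predicted at 336 weeks |
|---|---|---|---|---|
| 0 | 550 m | 63.6 | 0.0 | 63.6 |
| 5 | 550 + 23.0 = 573.0 m | 61.1 | -2.6 | 350/582.2 = 60.1 |
| 10 | 550 + 46.0 = 596.0 m | 58.7 | -4.9 | 350/614.4 = 57.0 |
| 20 | 550 + 92.0 = 642.0 m | 54.5 | -9.1 | 350/678.8 = 51.6 |

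Raw change is 0 m in every row. The g = 0 row stands for a patient whose growth is complete.

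**The case against.** **Silence may not be a conflict.** The precedence rule applies only where the documents conflict, and SAP section 7 names the test it removes without naming this summary. A reader might infer that the analysis will certainly not be done; the documents do not say so. What stands is that its status is undefined. Under one reading it is lost without a reason; under the other it is owed, but with no equation.

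**The endpoint is intact.** Protocol 3.3 and SAP 3.3 both define the secondary endpoint as change in 6MWD, and SAP 5.8.1 analyses that. A reader might infer that an endpoint has been dropped. It has not: what is missing is a supporting analysis, in a study whose primary objective is safety.

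**Partial safeguards exist.** Distance is summarised by actual age in Study 019 (SAP 5.8.1) and in the matched natural-history data (SAP 8.2.1). Timed function tests, NSAA and age at loss of ambulation are read as well. The formal natural-history comparisons in SAP 8.2.1 are FVC, age at loss of ambulation and age at FVC below 1 liter, so raw 6MWD is not among them. These points lower the stakes, but they do not separate growth from a boy's change in meters.

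**The size is assumed.** This is correct. The range must include zero, since the SAP has age groups of 12-17 and 18 or over.

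**The 30 m figure.** A reader might set the illustration against the 30 m difference cited in the protocol. That comparison is not supported. The 30 m is Study 007's between-arm difference from placebo at Week 48 (protocol 1.1 and 14.2), not a benchmark for growth within a patient over 240 weeks. Even at the top assumed rate, 48 weeks (0.92 years) gives only 20 × 0.92 × 350/550 = 11.7 m.

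**Conclusion.** The omission and its absence from SAP section 7 are plain from the text. A pre-specified supporting analysis of a secondary endpoint is at risk of being lost with no stated reason, and it should be restored or its removal justified.

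The consequence is a possibility. In boys still growing, raw change can hide part of the decline; where growth is complete it hides almost nothing. It would go too far to say that the planned results do hide decline, because the documents contain no growth data, reference equation or walk results to show it.

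On the assumed 550 m start and a rise of 0 to 20 m per year, a boy flat at 350 m loses 0 to 9.1 percentage points of predicted distance over 240 weeks. The same inputs give 0 to 12.1 points over 336 weeks (63.6 - 51.6, from unrounded values). Both ranges depend wholly on those inputs.

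**What to change.** In SAP 5.8.1, restore the descriptive summary of percent-predicted 6MWD, as observed value and change from baseline by visit, beside the summary in meters. Name one reference equation before the analysis, and use the height measured at the same visit as the walk. Do not carry the last height forward: that freezes height in boys who may still be growing. Where a visit has a walk but no height, leave the derived value missing and report how many there are.

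An MMRM on this variable is optional, since the protocol did not ask for one. If added, its baseline covariate and baseline categories must be redefined in percent-predicted units. The paired t-test need not return, because SAP section 7 already records its removal.

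If the analysis is left out on purpose, say so in SAP section 7 and give the reason.

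The cost is one derived variable, one table and a few lines of SAP text, with no new data collection. The downside for the sponsor is that the results may look less favourable than meters alone.
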